Study Rationale	
Multiple myeloma constitutes approximately 10% of all hematologic malignancies. High dose chemotherapy followed by autologous HCT remains an integral treatment strategy for multiple myeloma. Lenalidomide is the most commonly prescribed maintenance therapy after autologous HCT, however, disease relapse/progression after autologous HCT remains unavoidable secondary to the existence of minimal residual disease and drug resistance conferred by tumor microenvironment. When patients relapse/progress after autologous HCT, management of disease depends on prior treatment history, organ function and patient tolerability to certain chemotherapeutic agents. There are considerable practice variations in part due to several FDA approved anti-myeloma agents and there is no consensus on how best to treat serologic relapse/progression without symptomatic disease after autologous HCT.
 
With the incorporation of free light chain assay into the standard clinical practice, relapse/progression of myeloma may be captured early and only limited literature is available to characterize the pattern of relapse/progression after autologous HCT. A Spanish group reported 4 distinctive patterns of relapse/progression including (1) extramedullary disease, (2) plasma cell leukemia, (3) clinically symptomatic disease (66%), and (4) insidious increase in serum M-spike (18%).⁵ More recently, Zamarin et al. evaluated 273 patients who underwent autologous HCT (79% of them not on maintenance) and showed that 85% of patient had asymptomatic relapse/progression detected by serologic testing whereas only 15% had symptomatic relapse/progression (characterized by anemia, renal failure, hypercalcemia, soft tissue or bone disease) after autologous HCT.⁶ The latter study demonstrated increasing frequency of serologic relapse without symptomatic disease after autologous HCT over time. It was also shown that the survival was better with asymptomatic relapse/progression.⁶ A Spanish group conducted an observation prospective registry study evaluating the timing and pattern of relapsed disease in myeloma patients.⁷ The median time from biological/serologic relapse to clinical (symptomatic) relapse was 105 days which is relatively short.⁷ Signaling Lymphocyte Activation Molecule family-7 (SLAMF7, also known as CS1 or CD319) is a human membrane glycoprotein and member of the immunoglobulin superfamily.^{8,9} SLAMF7 is expressed on myeloma cell surface on both primary human myeloma cells and myeloma cell lines.⁹ Soluble SLAMF7 has also been detected in myeloma patients' serum and has been shown to correlate with myeloma disease stage.⁸ Additionally, SLAMF7 is expressed in natural killer (NK) cells and T-cell subsets.^{10,11} The CS1/SLAMF7 gene is located on the long arm of chromosome 1 (1q23.1-1q24.1), and gains of chromosome 1q are relatively frequent in myeloma.¹² SLAMF7 has been demonstrated to co-localize with CD138 promoting cell-cell adhesion, and plays a role in myeloma cell interactions with bone marrow stromal cells.^{8,13} SLAMF7 is a self-ligand for NK cells and promotes activation through selective expression of the adaptor protein, EAT-2.¹⁴⁻¹⁶ Furthermore, SLAMF7 may inhibit T cells that lack EAT-2.¹⁴ Elotuzumab (previously called HuLuc63) is a humanized immunoglobulin G₁ anti-CS1/SLAMF7 monoclonal antibody that has been shown to impair myeloma cell adhesion. In vitro studies

	have shown impaired primary myeloma cell survival with or without bone marrow stromal cells. ⁸ Elotuzumab is thought to exert effects on myeloma cells through antibody-dependent cellular cytotoxicity (ADCC) which is mediated by NK cells through interaction of their Fcγ RIIia receptor. ^{8,9,17} Elotuzumab also directly activate NK cells through direct SLAMF7 ligation. ^{18,19} In a phase 1 dose escalation study of Elotuzumab in 35 advanced myeloma

	
patients, there was no maximum tolerated dose (MTD) identified up to 20 mg/kg (given every 14 days for 8 weeks).²⁰ Nine out of 34 patients (26.5%) had stable disease at day 56, suggesting limited single agent activity. At doses of 10 and 20 mg/kg of Elotuzumab, SLAMF7 receptors on bone marrow-derived myeloma cells were consistently saturated.²⁰ Mean terminal phase half-life increased with a dose escalation ($T_{1/2} \square$ of 7.8 days with 20 mg/kg) suggesting a saturation of target-mediated elimination.²⁰ Transient decreases in lymphocyte counts were observed (within hours, in both CS1⁺ and CS1⁻ subsets) but returned to baseline levels by day 7.²⁰ Several phase II and III trials using combination therapy with Elotuzumab have been conducted in myeloma.²¹ Most recently, a phase 3 trial comparing Elotuzumab (10 mg/kg days 1, 8, 15, and 22 for first 2 cycles, then on days 1 and 15 with third cycle), lenalidomide and dexamethasone with lenalidomide plus dexamethasone in relapsed/refractory myeloma has been reported.¹ After a median follow-up of 24.5 months, median progression-free survival (PFS) was 19.4 months in Elotuzumab group vs. 14.9 months in control group ($P < 0.001$).¹ This very promising anti-CS1/SLAMF7 monoclonal antibody therapy with Elotuzumab has now been FDA approved and added to the armamentarium of anti-myeloma therapy. Overall, Elotuzumab appears to be well tolerated, with most common adverse events with single agent therapy being infusion-related reactions.²² In the phase 3 trial, Elotuzumab group had higher grade 3-4 lymphopenia (77% vs. 49%).¹ There was also a suggestion that grade 3 or 4 neutropenia incidence may be lower in Elotuzumab group (34% vs. 44%). Based on the prior clinical studies of Elotuzumab in relapse/refractory myeloma, Elotuzumab was demonstrated to be safe and effective for its treatment at a dose of 10 mg/kg in combination with lenalidomide.
 
As noted previously, it is critical that the Fc portion of Elotuzumab is able to bind to the FcγRIIIa receptor expressed on NK cells.^{8,9} The FcγRIIIa gene has allelic variation that determines the affinity of the FcγRIIIa receptor for IgG1 antibodies such as elotuzumab.⁹ In a phase 2 study of Elotuzumab plus bortezomib/dexamethasone for relapse/refractory multiple myeloma, Jakubowiak et al. evaluated the associations of FcγRIIIa receptor polymorphisms and clinical outcomes.²³ Patients who were homozygous for the high-affinity FcγRIIIa V (VV) allele had a longer PFS compared to those with homozygous for the low affinity FcγRIIIa F (FF) allele (22.3 months vs. 9.8 months),²³ suggesting the importance of evaluation FcγRIIIa polymorphisms to predict better disease control in subsets of myeloma patients. Of note, this advantage in the VV group for FcγRIIIa was not seen when Elotuzumab was combined with lenalidomide and dexamethasone in the Eloquent-2³⁹.
 
Disruption of interactions between myeloma cells and the microenvironment by targeting SLAMF7 using Elotuzumab (anti-CS1/SLAMF7 monoclonal antibody) could potentially abrogate drug-resistance and sensitize cells that are losing response to lenalidomide. Elotuzumab could potentially increase the NK cell activity in the context of lenalidomide therapy. We hypothesize that addition of Elotuzumab to myeloma patients who demonstrate serologic relapse/progression to single agent lenalidomide maintenance may modulate antimyeloma immune response and render those patients into better response and prolong time to progression.

Primary Objectives	Progression free survival with Elotuzumab plus lenalidomide when Elotuzumab is added to multiple myeloma patients with serologic relapse/progression while receiving lenalidomide maintenance for each cohort

Secondary Objectives	
Overall response rate (ORR) with Elotuzumab and lenalidomide for each cohortMinimum response (MR) or better rate with Elotuzumab and lenalidomide for each cohortTime to next treatment (TTNT) for each cohortComparison of clinical outcomes (cohort A versus B)Fcγ RIIIA receptor polymorphisms (homozygous for high-affinity V (VV) allele vs. low affinity F (FF) allele)Effect of Elotuzumab added to lenalidomide on phenotypic characteristics of the immune infiltrate and correlation with therapeutic efficacy
Sample Size	
In a randomized phase 2 study of lenalidomide single agent therapy (either 30 mg daily or 15 mg PO twice daily days 1-21 out of 28-day cycle) in relapsed/refractory myeloma where dexamethasone was added after 2 cycles if progressive or stable disease, median PFS was 7.7 months with once-daily lenalidomide (compared to 3.9 months with twice daily lenalidomide).²⁴ In a phase 3 study, a combination of Elotuzumab/lenalidomide/dexamethasone vs. lenalidomide/dexamethasone in relapsed/refractory myeloma showed PFS of 19.4 months vs. 14.9 months (with 5 months benefit).¹ Based on these results, we assume that in patients receiving single agent lenalidomide maintenance even if the dose of lenalidomide was increased to the maximum dose of 25 mg PO daily, those patients who are experiencing serologic relapse/progression would have at best 7 months of median PFS and a Spanish study indicated approximately 3 months until clinical progression (without any study). We hypothesize that the addition of Elotuzumab to maintenance lenalidomide would improve PFS to 12 months (with addition of 5 months benefit). We anticipate that approximately 3 subjects per month will be accrued over 24 months. The statistical power was computed based on the assumptions; (1) null PFS of 7 months and alternative PFS of 12 months, (2) the projected accrual of 24 months, (3) a follow-up time of 12 months, and (4) an one-sided alpha of 0.05. With these assumptions, a sample size of 30 patients per cohort would have 85% power to reject the null hypothesis of 7 months (versus alternative of 12 months, hazard ratio 0.58). As the primary goal of the study is to investigate the clinical benefit of each combination regimen, results of the cohort (A) and cohort (B) will be reported separately and additional comparative analyses will be performed as an exploratory aim. The final analysis for primary endpoint will be conducted if 28 PFS events are observed.

Study Design	
Randomized parallel 2-cohort phase 2 study of Elotuzumab given at 10 mg/kg weekly during induction in combination with lenalidomide (either 25 mg or 10 mg) in patients with multiple myeloma who progress or relapse serologically while on single agent lenalidomide maintenance. Patients will be randomized to either (1) cohort A = lenalidomide 25 mg PO daily days 1-21 with Elotuzumab or (2) cohort B = lenalidomide 10 mg PO daily days 1-21 with Elotuzumab. We selected the dose of Elotuzumab at 10 mg/kg weekly dosing followed by monthly infusion of 20 mg/kg based on the safety and tolerability profile in the published phase 3 study and other studies of combination therapy with bortezomib,¹⁻³ as well as an ongoing study in combination with pomalidomide (NCT02612779). Elotuzumab will be administered intravenously on days 1, 8, 15, and 22 during the first 2 cycles, then on day 1 of each cycle starting third cycle. The combination therapy with Elotuzumab and lenalidomide will be continued until further progression of myeloma (based on response criteria) or intolerance.
 
Combination dosing schedule:

--------------	---

	
(1) Cohort A:
 
 • Elotuzumab 10 mg/kg IV weekly (days 1, 8, 15 and 22) for 2 cycles, then 20 mg/kg every 4 weeks • Lenalidomide 25 mg PO daily days 1-21 out of a 28-day schedule 
(2) Cohort B:
 
 • Elotuzumab 10 mg/kg IV weekly (days 1, 8, 15 and 22) for 2 cycles, then 20 mg/kg every 4 weeks • Lenalidomide 10 mg PO daily days 1-21 out of a 28-day schedule 
 
Cohort (A): N=30
 
 • Elotuzumab • Lenalidomide 25 mg 
 
 C#1	C#2	C#3	C#4	C#5	C#6	
 
 						
 
 						
 
 
 
 
Cohort (B) : N=30
 
 • Elotuzumab • Lenalidomide 10 mg 
 
 C#1	C#2	C#3	C#4	C#5	C#6	
 
 						
 
 						
 
 
 
Response assessment:
 
The Consensus on Uniform Reporting of Response will be used to evaluate response.⁴ Myeloma patients enrolled in this clinical study will be assessed for disease response after every cycle. Time to disease progression will be defined as the time from the day first Elotuzumab treatment to the time of myeloma progression.
	C#1	C#2	C#3	C#4	C#5	C#6													C#1	C#2	C#3	C#4	C#5	C#6												
C#1	C#2	C#3	C#4	C#5	C#6																																
C#1	C#2	C#3	C#4	C#5	C#6																																

Duration of Treatment
 
1.1.1 Clinical 1.1.2 relapse
 
1.1.3
	
Patients will continue on therapy until clinical relapse as per IMWG criteria;
 
Clinical relapse requires one or more of the following criteria:
 
Direct indicators of increasing disease and/or end organ dysfunction (CRAB features) related to the underlying clonal plasma-cell proliferative disorder. It is not used in calculation of time to progression or progression-free survival but is listed as something that can be reported optionally or for use in clinical practice;
																																				

Protocol	Confidential	Elotuzumab/Lenalidomide
	1.1.4	Development of new soft tissue plasmacytomas or bone lesions (osteoporotic fractures do not constitute
	1.1.5 1.1.6 1.1.7 1.1.8 1.1.9	progression); Definite increase in the size of existing plasmacytomas or bone lesions. A definite increase is defined as a 50% (and ≥ 1 cm) increase as measured serially by the SPD ^{§§} of the measurable lesion; Hypercalcemia (>11 mg/dL); Decrease in hemoglobin of ≥ 2 g/dL not related to therapy or other non-myeloma-related conditions; Rise in serum creatinine by 2 mg/dL or more from the start of the therapy and attributable to myeloma; Hyperviscosity related to serum paraprotein

Lancet Oncol 2016; 17: e328–46

Inclusion/ Exclusion criteria	Inclusion criteria
	
1. Patients with multiple myeloma who demonstrate evidence of serologic relapse/progression while on lenalidomide maintenance given as part of first line therapy (including upfront high-dose chemotherapy followed by autologous hematopoietic cell transplantation (HCT)) without symptomatic relapse/progression. Lenalidomide maintenance is defined as single agent lenalidomide therapy of any doses up to 15 mg PO daily for 14-28 days (28-day cycle). Relapse/progression is defined as increase of 25% from lowest confirmed response value in one or more of the following criteria: Serum M –protein (absolute increase must be \geq 0.5g/dl) Serum M-protein increase >1g/dl, if the lowest M component was >5 g/dl Urine M –protein (absolute increase must be > 200 mg in 24 hours) In patients without measurable serum and urine M-protein levels, the difference between involved and uninvolved FLC levels (absolute increase must be > 10 mg/dl) For patients relapsing from complete remission, relapse is defined as: Reappearance of serum or urine M-protein by immunofixation or electrophoresis.2. Male or female patients aged ≥ 18 years old3. Ability to provide written informed consent obtained prior to participation in the study and any related procedures being performed4. Measurable disease with at least 1 of the following assessed within 28 days prior to Cycle 1 Day 1:
a. Serum M-protein ≥ 0.5 g/dL,b. Urine M-protein ≥ 200 mg/24 hour,c. In subjects without detectable serum or urine M-protein, serum free light chain (SFLC) > 10 mg/dL (involved light chain) and an abnormal serum kappa lambda ratio5. Patients must meet the following laboratory criteria within 28 days prior to Cycle 1, day 1:

	
a) Absolute neutrophil count (ANC) $\geq 1 \times 10^9/L$b) Hemoglobin $\geq 10 \text{ g/dL}$c) Platelet count $\geq 75,000/\text{mm}^3$d) AST and ALT $\leq 2.5 \times \text{ULN}$e) Serum bilirubin $\leq 1.5 \times \text{ULN}$f) Serum Creatinine clearance $\geq 50\text{ml/min}$
	
Exclusion criteria
 
1. Prior Elotuzumab2. Patients with clinical relapse/progression as per the IMWG uniform criteria defined as one or more of the following criteria:
a. Development of new soft tissue plasmacytomas or bone lesions (osteoporotic fractures do not constitute progression)b. Definite increase in the size of existing plasmacytomas or bone lesions. A definite increase is defined as a 50% (and $\geq 1 \text{ cm}$) increase as measured serially of the measurable lesionc. Hypercalcemia ($>11 \text{ mg/dL}$);d. Decrease in hemoglobin of $\geq 2 \text{ g/dL}$ not related to therapy or other non-myeloma related conditions;e. Rise in serum creatinine by 2 mg/dL or more from the start of the therapy and attributable to myelomaf. Hyperviscosity related to serum paraprotein3. Women who are pregnant or breast feeding or women of childbearing potential (WOCBP) not using an effective method of birth control. WOCBP are defined as sexually mature women who have not undergone a hysterectomy or who have not been naturally postmenopausal for at least 12 consecutive months (i.e., who has had menses any time in the preceding 12 consecutive months). Women of childbearing potential must have a negative serum pregnancy testing within 7 days prior to the administration of drug.4. Male patients whose sexual partners are WOCBP not using effective birth control5. Patients with a prior malignancy within the last 5 years (except for skin basal or squamous cell carcinoma, or in situ cancer of the cervix)6. Patients with known positivity for human immunodeficiency virus (HIV) or hepatitis C; baseline testing for HIV and hepatitis C is not required7. Patients with a diagnosis of POEMS syndrome (polyneuropathy, organomegaly, endocrinopathy, monoclonal protein, and skin changes) or plasma cell leukemia ($> 2.0 \times 10^9/\text{L}$ circulating plasma cells by standard differential)

Screening Assessments (to be done within 28 days of C1D1)	Signed written informed consent Demographics and medical history (prior therapy) Pregnancy test (if applicable) Physical examination and vital signs (within 28 days of therapy)
	Hematology (CBC) (within 28 days of therapy) Clinical chemistry (within 28 days of therapy) Assessment of disease status (within 28 days of therapy) (SPEP, 24h UPEP, serum free light chain) Bone marrow aspiration and biopsy with cytogenetics, FISH, My PRS (gene expression profile) (within 28 days of therapy) Skeletal survey (within 28 days of therapy) Concomitant medication
Treatment and post treatment assessments	Day 1 of each cycle Physical examination and vital signs CBC (also day 8, 15, 22 of cycles 1-2) Complete clinical chemistry (also day 8, 15, 22 of cycles 1-2) Assessment of disease status (SPEP, 24h UPEP, Quantitative Immunoglobulins, serum free light chain) Adverse events and concomitant medication Pregnancy test if applicable
Response	Response will be assessed per the uniform response criteria of the IMWG
Safety variables and analysis	The safety and tolerability of Elotuzumab and lenalidomide given for the treatment of serologic progression after first line therapy to myeloma patients will be evaluated by means of AE reports, physical examinations, and laboratory safety evaluations. Common Terminology Criteria for Adverse Events (CTCAE) V 5.0 will be used for grading of AEs. Investigators will provide their assessment of causality as 1) unrelated, 2) unlikely related, 3) possibly related, or 4) probably or 5) definitely related for all AEs to one both study drugs.

Table of Contents

1.1 Overview and Study Rationale	13
1.2 Overview of Elotuzumab	14
1.2.1 Combination studies of Lenalidomide and elotuzumab	15
2 Study objectives	16
2.1 Primary Objective	16
2.2 Secondary Objectives	16
3 Overall study design	16
4 Study population	18
4.1 Inclusion criteria	18
4.2 Exclusion criteria	19
5 Treatments	20
5.1 Investigational therapy	20
5.2 Treatment cycle and duration	21
5.6 Interruption or discontinuation of treatment	23
5.7 Dose modifications for elotuzumab	23
5.8 Dose modifications for lenalidomide-related toxicity	23
5.9 Study drug discontinuation	24
5.10 Other concomitant medications	25
5.11 Treatment compliance	26
6 Visit schedule and assessments	26
6.1 Visit schedule	26
6.2 Efficacy assessments	28
6.3 Safety assessments	28
6.3.1 Adverse events	29
6.3.2 Vital signs	29
6.3.3 Physical examination	30
6.3.4 Laboratory evaluations	30
7 Statistical methods	32
7.1 Primary Efficacy Analysis	32
7.2 Secondary Endpoints Analyses	33
8 REGULATORY CONSIDERATIONS	33
8.1 Institutional Review Board/Ethics Committee Approval	33
8.2 Informed Consent	33

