5.1 Investigational therapy

Elotuzumab will be provided by BMS as investigational product. Elotuzumab (BMS-901608, also known as HuLuc63) is an immune-stimulatory humanized, IgG1 monoclonal antibody (mAb) targeted against signaling lymphocyte activation molecule family 7 (SLAMF7), a glycoprotein expressed on myeloma and natural killer (NK) cells. EMPLICITI™ (Elotuzumab) is commercially available and is indicated in combination with lenalidomide and dexamethasone for the treatment of patients with multiple myeloma who have received one to three prior therapies. All precautions and restrictions included in the Prescribing Information (e.g., pregnancy testing and contraception) must be observed when dispensing and administering lenalidomide as part of this protocol. During the study, Elotuzumab will be administered in combination with lenalidomide at a dose of 10 mg/kg administered intravenously every week for the first two cycles and at a dose of 20 mg/kg monthly thereafter until disease progression or unacceptable toxicity.

Product Description / Class and Dosage Form	Potency	IMP/NonIMP	Blinded or Open Label	Packaging / Appearance	Storage Conditions (per label)
Elotuzumab Powder for Solution for Infusion	400 or 300 mg/vial	IMP	Open Label	Vial	Refer to the label on container

Lenalidomide is a thalidomide analogue indicated for the treatment of subjects with multiple myeloma, in combination with dexamethasone, in subjects who have received at least 1 prior therapy.

Lenalidomide is a commercially available drug, available for oral administration, depending upon local health authority approvals ([Celgene Corporation 2013](#)).

All precautions and restrictions included in the Prescribing Information (e.g., pregnancy testing and contraception) must be observed when dispensing and administering lenalidomide as part of this protocol.

During the study lenalidomide will be administered at 10 or 25 mg PO daily days 1-21 of 28 days cycles until disease progression or discontinuation.

Dexamethasone is a commercially available drug. The description, how supplied, and storage instructions for dexamethasone product are found in the prescribing information.

During the study dexamethasone will be administered as premedication for Elotuzumab as indicated in the package insert.

Treatment assignment

Patients will be randomized to either (1) cohort A = lenalidomide 25 mg PO daily days 1-21 or (2) cohort B = lenalidomide 10 mg PO daily days 1-21 with Elotuzumab.

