5.2 Treatment cycle and duration

Treatment cycles will have a duration of 28 days and subjects will receive Elotuzumab on days 1,8,15, and 22 of cycles 1-2 and on day 1 on cycle 3 and beyond, in combination with lenalidomide at either 25 mg (cohort A) or 10 mg (cohort B) on days 1-21. All cycles will start 28 days (\pm 3) after the start of the prior cycle.

Subjects will continue therapy until one of the following:

1. Disease progression
2. Withdrawal from the study for any reason
3. Death

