5.9 Study drug discontinuation

It will be documented whether or not each patient completed the clinical study. If for any patient either study treatment or observations were discontinued, the reason will be recorded.

Reasons that a patient may discontinue treatment are considered to constitute one of the following:

1. Subject's condition no longer requires study treatment (e.g. satisfactory therapeutic response)
2. Clinical relapse/progression as per the IMWG uniform criteria defined as one or more of the following criteria:
 - a. Development of new soft tissue plasmacytomas or bone lesions (osteoporotic fractures do not constitute progression)
 - b. Definite increase in the size of existing plasmacytomas or bone lesions. A definite increase is defined as a 50% (and ≥ 1 cm) increase as measured serially of the measurable lesion
 - c. Hypercalcemia (> 11 mg/dL);
 - d. Decrease in hemoglobin of ≥ 2 g/dL not related to therapy or other non-myeloma-related conditions;
 - e. Rise in serum creatinine by 2 mg/dL or more from the start of the therapy and attributable to myeloma
 - f. Hyperviscosity related to serum paraprotein
 - g. Adverse event(s)
 - h. Abnormal laboratory value(s)

- i. Abnormal test procedure result(s)
- j. Protocol violation
- k. Subject withdrew consent
- l. Lost to follow-up
- m. Administrative problems
- n. New cancer therapy
- o. Death

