6.2 Efficacy assessments

Response will be determined by the investigator based on the disease assessments described above and the IMWG-URC (see definitions in [Appendix B](#)). Myeloma response will be assessed at the beginning of each cycle.

The following confirmatory assessments are required for all response categories (stringent complete response [sCR], CR, VGPR, and PR) and progressive disease:

- All laboratory-based progressive disease and all responses require 2 consecutive assessments made at any time before initiation of any new therapy. Confirmatory lab samples should be separated by at least 1 calendar day
- Progressive disease by nonlaboratory-based assessment (i.e.; plasmacytoma or skeletal lesion) does not require confirmatory report
- All response categories also require no evidence of progression including new bone lesions if radiographic studies were performed
- Confirmation of CR or sCR requires bone marrow biopsy or aspirate slides (a confirmatory bone marrow sample is not required)
- Extramedullary plasmacytoma evaluation (if present at baseline)

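### The protocol gives two incompatible disease triggers for stopping treatment: IMWG clinical relapse in the synopsis Duration of Treatment row, and progression by response criteria in the Study Design row and section 3

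*Combined protocol and SAP*

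**What the plan says.** Six places in the protocol bear on when disease ends treatment.

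- **Synopsis, Duration of Treatment:** "Patients will continue on therapy until clinical relapse as per IMWG criteria". The row then lists the clinical-relapse features and notes that clinical relapse does not enter the calculation of time to progression or PFS.
- **Synopsis, Study Design, and section 3 (same sentence):** combination therapy "will be continued until further progression of myeloma (based on response criteria) or intolerance".
- **Section 5.1:** elotuzumab is given "until disease progression or unacceptable toxicity" and lenalidomide "until disease progression or discontinuation". Progression is not defined there.
- **Section 5.2:** "Subjects will continue therapy until one of the following", followed by disease progression, withdrawal for any reason, and death. Progression is again undefined.
- **Section 5.9:** "Reasons that a patient may discontinue treatment are considered to constitute one of the following". The only disease-worsening entry is "Clinical relapse/progression as per the IMWG uniform criteria defined as one or more of the following criteria", with the clinical features listed. Abnormal laboratory values also appear in the list.

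Section 6.2 recognises progression on laboratory grounds alone: "All laboratory-based progressive disease and all responses require 2 consecutive assessments made at any time before initiation of any new therapy". Appendix B has one row for progressive disease and another for clinical relapse.

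**The concern.** Clinical relapse and progressive disease are different events in the protocol's own appendix, and the second can occur without the first. A site reading the Duration of Treatment row would keep dosing a patient whose M-protein has risen enough to count as progression. A site reading the Study Design row or section 3 would stop.

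The patient concerned is foreseeable. Inclusion criterion 1 admits patients on serologic progression, exclusion criterion 2 removes those with clinical relapse, and section 6.4 repeats the disease markers on day 1 of each cycle. Laboratory progression seen before any clinical feature is the same kind of state in which patients enter the trial.

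At stake are whether a progressed patient is dosed again, the exposure that results, and when the safety windows tied to treatment close. Those windows are adverse event collection while on study treatment (6.3.1), follow-up for at least 4 weeks after the last dose (5.9.1.1), and serious adverse event reporting through 30 days after dosing stops (9.4.2).

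**Working it through.** No stated figure depends on this point, so the check compares the rules for one patient.

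**Test patient.** Serum M-protein has risen by at least 25% and by at least 0.5 g/dL from its lowest confirmed value. The rise is confirmed on two consecutive assessments as section 6.2 requires. There is no new or growing plasmacytoma or bone lesion, hypercalcemia, qualifying hemoglobin fall or creatinine rise, hyperviscosity, or other sign of end-organ damage.

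**Classification under Appendix B.** The progressive disease row is met, since any one of its criteria is enough. The clinical relapse row is not met, since it needs at least one clinical feature.

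| Place | Trigger | Instruction for this patient |
|---|---|---|
| Synopsis, Duration of Treatment | IMWG clinical relapse | Continue |
| Synopsis, Study Design | Progression by response criteria | Stop |
| Section 3 | Progression by response criteria | Stop |
| Section 5.1 | Disease progression, undefined | Stop if progression means IMWG progressive disease |
| Section 5.2 | Disease progression, undefined | Stop if progression means IMWG progressive disease |
| Section 5.9 | Clinical relapse, in a permissive list | Leans to continue; requires neither |

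No statement gives one rule precedence over the other or reconciles them.

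**Consequences for the analysis.**

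- *Power.* The 85% rests on medians of 7 and 12 months, 24 months of accrual, 12 months of follow-up, one-sided alpha 0.05 and 30 patients per cohort. The stopping rule is not an input.
- *PFS date.* If the event is IMWG progressive disease, dosing given after it cannot move its date. The note in the Duration of Treatment row, the same note in Appendix B and the Appendix B footnote on progressive disease largely imply this reading. Section 7.1 says only relapse or progression, so it is not stated outright.
- *Time to next treatment.* Section 5.10 requires withdrawal before other anticancer agents are given, so a longer stay on study drug could delay the next therapy. The documents give nothing from which to size this.
- *Exposure.* The number of extra cycles is not given. It is zero for a patient whose progression is first seen clinically.

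**The case against.** Three arguments on the other side deserve weight.

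First, the two rules might be read together. The Appendix B table is headed as response criteria and contains the clinical relapse row as well as the progressive disease row, so the Duration of Treatment row could be taken as the specific definition of progression for stopping. This is possible but strained. Section 6.2 treats laboratory-based progressive disease as an event in its own right, and Appendix B keeps clinical relapse out of the PFS calculation. A site should not have to infer the rule.

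Second, the discretion in sections 5.2 and 5.9 lets an investigator stop at any point. That is so, but permission to stop does not tell sites which rule applies, and two sites could treat the same patient differently while both comply.

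Third, the safety windows follow actual dosing, so no administered dose goes unobserved under either rule. This stands. The windows will differ in length between patients handled differently, but they leave no gap in coverage.

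A reader might also infer that the Duration of Treatment row is simply a slip and that stopping at progression is the settled intent. The documents do not establish this. Section 5.9 uses clinical relapse, section 6.4 times the late marrow at clinical relapse, and sections 5.1 and 5.2 leave progression undefined. Only one sentence, appearing twice, ties stopping to response criteria.

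**Conclusion.** The inconsistency is real and should be corrected. For a patient with confirmed laboratory progression and no clinical-relapse feature, the Duration of Treatment row and the Study Design row with section 3 cannot both be followed. The effect falls on dosing after progression, exposure and the end of on-treatment adverse event collection.

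Two larger readings are tempting and are not supported. One is that the primary analysis is compromised. Power does not depend on the stopping rule, and the PFS date is unaffected provided IMWG progressive disease is the event. The other is that the extra treatment can be sized from the registry median of 105 days between serologic and clinical relapse cited in the background (105 / 28 = 3.75 cycles). That figure does not describe patients on this regimen. The number of patients affected, the extra cycles and any shift in time to next treatment remain unknown.

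The conclusion rests on reading progression based on response criteria as the Appendix B progressive disease row, which is the natural reading.

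**What to change.** Choose one trigger and state it in the same words in the synopsis Duration of Treatment and Study Design rows and in sections 3, 5.1 (both drugs), 5.2 and 5.9.

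- **Simplest choice:** confirmed IMWG progressive disease. This matches the only wording tied to response criteria. The Duration of Treatment row and the clinical-relapse item in 5.9 change; 5.1 and 5.2 need only the definition.
- **If treatment past serologic progression until clinical relapse is intended:** say so explicitly in the Study Design row and in sections 3, 5.1 and 5.2, and make 5.9 agree.

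Under either choice, add a sentence to 7.1 that the PFS event is the first confirmed IMWG progressive disease or death, whether or not study treatment continues. Keep the exemption in 6.2 under which non-laboratory progression needs no confirmation. Then time the progression marrow consistently with the chosen rule: section 6.4 now says clinical relapse, while Table 6-1 footnote 1 and section 6.5 say progression.

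The cost is a wording amendment. Stopping at progressive disease adds no procedures. Treating past progression adds exposure. At nominal doses from cycle 3, each further cycle brings one 20 mg/kg elotuzumab infusion, 28 + 8 = 36 mg of dexamethasone premedication, and 25 x 21 = 525 mg of lenalidomide in cohort A or 10 x 21 = 210 mg in cohort B. These are per-cycle costs of that choice, not an estimate of the present problem's size.
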